## **3.2. Sample Size Justification**

The planned sample size for the study is 972 randomized participants (324 for each of the three study groups). The binomial regression analysis described for the binary outcomes of Specific Aim 1 drive this sample size calculation because binary outcomes contain the least amount of information (and hence, yield the lowest statistical power). The assumptions that lead to this sample size of 972 randomized participants are as follows:

1. binomial regression with the proportion of occurrences out of four time points
2. 90% statistical power
3. two-sided, 0.025 significance level test (Bonferroni correction) comparing RLP to control, RLP+ to control, and RLP to RLP+ within each stratum
4. effect size of 0.10 (difference between rates of 0.25 and 0.35)
5. 10% lost to follow-up per year, 10% lost per year for women who change their minds about intending pregnancy, and another 10% lost per year for those women who become pregnant (intentionally or unintentionally)

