### **5.2.3. Drop-out Recovery Efforts**

If participants have not completed their scheduled survey by the date due, they will receive a series of reminders at one-week intervals as follows:

- 1st E-mail reminder that they are now due to complete their survey.
- 2nd e-mail reminder that they are due to complete their survey but time is running out. Email will also be sent to any secondary email addresses they listed at enrollment.
- Telephone call asking if participants have received our reminders and, depending upon their response, asking for an updated email address, asking them to check their junk folder, or sending them a new link.
- Text message stating that we have lost touch and asking participant to please call or email with updated contact information.
- Mailed letter stating that we have lost touch and to please call or email with updated contact information.

A final email will be sent out one week prior to taking the survey off line. The email will state that participation is very important and alert them to the fact that the survey will be taken off line by a given date.

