### 11.2. Analysis Plans

#### 11.2.1. Primary Outcome Variable (Aim 1)

##### 11.2.1.1. Contraceptive use

Using standard measurement, participants will be asked at each assessment if they are currently doing anything to prevent pregnancy (Y/N). The primary outcome measure for Aim 1 will be the proportion of 6-month intervals women are reporting any contraceptive use out of the number of 6-month intervals women are not intending pregnancy. Duration of contraceptive method use will also be assessed. Whether any contraception is being used is defined as a binary variable (yes/no) at each 6-month interval post-baseline (6, 12, 18, and 24 months). We will construct a proportion for each participant as the number of time periods in which the participant is using contraception, divided by the number of time periods in which the participant is not intending pregnancy.

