### 11.3. Analytic Methods

#### 11.3.1. Specific Aim 1

The outcome variables are binary (contraception use; satisfied with contraceptive method) and ordinal (contraceptive method effectiveness), and will be measured at four time periods post-baseline (6, 12, 18, and 24 months). For the binary outcome variables, we will construct a proportion for each participant as the number of time periods in which the participant's response is positive, divided by the number of time periods in which the participant is not intending pregnancy. The denominator will be four, except for those participants who withdraw consent from the study, change their minds about intending pregnancy during the study, or become pregnant. Therefore, we will apply a binomial regression analysis to these proportions. We will use intervention group assignment (intention-to-treat analysis) as the sole regressor in the primary analysis, but we will investigate in secondary analyses the effects of selected covariates on the proportional response (demographics; pregnancy history; sexual and contraceptive history; perceived control/fatalism toward contraception; relationships; compliance with log-in requirements). In terms of the three randomized groups, we will construct two-sided test statistics for comparing: 1) RLP to control, 2) RLP+ to control, and 3) RLP to RLP+. Therefore, we will impose a Bonferroni correction factor to the significance level ( $\alpha = 0.0167$ ). We will apply additional secondary analyses that are longitudinal, in which we invoke a logistic regression model with random participant effects to investigate if there are any time period effects and/or time period by intervention interactions for the binary outcomes. Finally, we will invoke a shared parameter model to account for the informative censoring that could occur due to participant withdrawal in a longitudinal study. In our setting, the shared parameter model includes a Weibull time-to-event regression model for the time to participant withdrawal in conjunction with a logistic regression model with random participant effects for the binary outcome.

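### The denominator rule for the primary proportion leaves out women who are lost to follow-up or miss a survey without withdrawing consent; read literally, their missed surveys count as contraceptive non-use

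*Protocol*

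**What the plan says.** Protocol section 11.2.1.1 defines the primary outcome as the "proportion of 6-month intervals women are reporting any contraceptive use out of the number of 6-month intervals women are not intending pregnancy". Section 11.3.1 builds the same proportion for both binary outcomes, contraceptive use and satisfaction with the method. Its numerator is "the number of time periods in which the participant's response is positive". Its denominator is the woman's count of periods without pregnancy intention. A working rule then follows: "The denominator will be four, except for those participants who withdraw consent from the study". Two further exceptions complete that list: a changed pregnancy intention, and pregnancy itself. Neither section says what happens to a survey that is not answered.

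Other sections expect unanswered surveys. The sample size assumptions in section 3.2 include "10% lost to follow-up per year", listed apart from 10% per year for changed intention and another 10% per year for pregnancy. Section 5.2.3 sets out a series of reminders for women who have not completed a survey, among them "Text message stating that we have lost touch", and then takes the survey offline.

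The shared parameter model in section 11.3.1 is an additional analysis. It models the time to withdrawal. The primary analysis is the binomial regression of the proportions on assigned group alone.

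**The concern.** The list of exceptions reads as complete, and loss to follow-up is not on it. A missed survey cannot yield a positive response, so it adds 0 above the line. If the denominator stays at four, it still adds 1 below the line. Arithmetically that is the same as a woman reporting that she used nothing.

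Two women with the same data would then score differently. Each reports use at 6 and 12 months and gives no data afterwards. If one formally withdraws and the other just stops answering, the first scores 2/2 = 1.00 and the second 2/4 = 0.50.

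At stake is the estimate of the primary outcome. Equal loss in the arms dilutes a true difference. Unequal loss moves the comparison directly, making the arm that answers less often look worse. The same rule governs the satisfaction outcome.

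**Working it through.** **Inputs from section 3.2:** rates 0.25 and 0.35; 90% power; two-sided alpha 0.025; four time points; 10% per year lost to follow-up, 10% per year changing intention, 10% per year pregnant; 324 women per arm, 972 in total. **Not stated:** the share of lost women who formally withdraw, loss by arm, and the within-woman correlation.

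**1. The plan's own sample size.** For one binary observation per woman, 0.25 versus 0.35 at these error rates needs 520 per arm. Four independent periods give 520/4 = 130. Removing 3 × 10% per year for two years, added up to 60%, gives 130/(1 − 0.60) = 325 per arm, or 975 against the stated 972. This match is not unique: a within-woman correlation of about 0.50 with no loss also gives 325. It is, however, consistent with section 3.2, which lists women lost to follow-up as lost. The literal rule in section 11.3.1 keeps them in the analysis with a denominator of four.

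**2. Share of surveys answered.** With constant loss of 10% per year, the share still answering at month m is 0.90^(m/12):

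| Month | 6 | 12 | 18 | 24 | Mean |
|---|---|---|---|---|---|
| Answering | 0.949 | 0.900 | 0.854 | 0.810 | 0.878 |

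On average 4 × (1 − 0.878) = 0.49 surveys per woman are missed.

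**3. Equal loss, literal rule.** Assume that no lost woman formally withdraws, that loss is unrelated to contraceptive use, and set changed intention and pregnancy aside. Then scored rate = true rate × 0.878:

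- control: 0.25 × 0.878 = 0.220
- intervention: 0.35 × 0.878 = 0.307
- difference: 0.100 × 0.878 = 0.088, an attenuation of about 12%.

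If every lost woman formally withdraws, the exception applies and the attenuation is 0. The range is therefore 0 to 12%.

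**4. Effect on power.** This is approximate: 324 per arm, four periods, alpha 0.025, variance factor (1 + 3ρ)/4 with an assumed correlation ρ.

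| ρ | Power at 0.25 vs 0.35 | Power at 0.220 vs 0.307 |
|---|---|---|
| 0.3 | 96% | 93% |
| 0.5 | 90% | 84% |
| 0.7 | 82% | 74% |

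**5. Unequal loss (assumed, not in the plan).** Take 10% per year in control and 15% in an intervention arm, with no true difference. With simple linear loss, the mean share missed is (5 + 10 + 15 + 20)/4 = 12.5% against 18.75%, a gap of 6.25 points. Spurious difference = −(true rate) × 0.0625:

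- at 0.25: −1.6 points
- at 0.35: −2.2 points
- at an assumed 0.90: −5.6 points (−5.3 with compounded loss as in step 2).

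**The case against.** The strongest reply is that the protocol nowhere says a missed survey is non-use. The sentence before the rule defines the denominator as periods in which the woman is not intending pregnancy. That state is learned from the survey, so for a missed survey it is unknown rather than counted. The statement that the denominator is four may only describe the usual case. Section 3.2 has a parallel list of three losses with loss to follow-up in the first place, which suggests that withdrawal of consent was loosely meant to cover it. The shared parameter model likewise treats withdrawal as censoring. This stands as far as intent goes: missed-as-non-use is a consequence of the wording, not a declared rule. It does not settle the wording. The two lists differ, and even the generous reading leaves out a woman who misses one survey and later returns. The shared parameter model is secondary and does not alter the primary regression. Nor is this a matter simply left to an analysis plan, because the protocol states the rule itself.

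Differential loss is also open to doubt. All arms answer the same surveys, and section 7.5.1 sends women to the intervention site only after the survey, so session length (about 30 minutes for RLP, 45 for RLP+) could affect later visits only. No figure in the document supports unequal rates.

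Two stronger readings are tempting and should not be drawn:

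- **A ratio above 1.** A reader might infer this from the shorter formula in section 11.2.1.1, "time periods in which the participant is using contraception, divided by the number of time periods in which the participant is not intending pregnancy", because its numerator carries no explicit restriction. But sections 3.1.1 and 11.1 describe use when not intending pregnancy, and the preceding definition in 11.2.1.1 counts intervals of use out of the not-intending intervals. The numerator is thus a subset of the denominator.
- **A bias as large as the planned effect.** Loss of 20% against 10% per year at 0.90 use would give 0.90 × 0.125 = 11 points. Neither input is in the plan. At the plan's rates the same loss gives 3.1 to 4.4 points.

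**Conclusion.** The rule is wrong as written and should be corrected, because it is part of the construction of the primary outcome. Taken literally, section 11.3.1 scores missed surveys as non-use, and as not satisfied, for women outside the three exceptions, while sections 3.2 and 5.2.3 plan for such women. With equal loss of 10% per year, the planned difference of 0.100 falls to between 0.088 and 0.100, depending on how many lost women formally withdraw. Under equal loss unrelated to use there is dilution but no spurious difference. A spurious difference of about 1.6 to 2.2 points at the plan's rates needs the assumed 15% versus 10% loss; it would be about 5 to 6 points if true use were 0.90, which is also an assumption.

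**What to change.** Reconcile the exception list in section 11.3.1 with the loss categories in section 3.2. In sections 11.2.1.1 and 11.3.1, state that numerator and denominator both count only completed surveys at which the woman is not intending pregnancy, and that missed surveys are treated as missing. Keep scoring missed surveys as non-use only as a labelled sensitivity analysis. Apply the same rule to the satisfaction outcome.

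The cost is about one sentence in each section, with no change to data collection. Under the assumptions of step 3, the difference of 0.100 is recovered. There is a small downside: women with no completed follow-up survey leave the primary analysis, about 5% of women (1 − 0.949) at 10% loss per year. Dropout related to contraceptive use could still bias the result. The planned shared parameter model should examine this, and the text should say that its withdrawal event includes loss to follow-up.

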### **7.2.4. Maintenance Phase**

At 6 month intervals (6-months, 12-months, 18-months), the RLP group will be emailed and asked to login to the website and participate in a “booster” of the intervention.

The RLP “booster” will allow the participant to view and confirm her previous reproductive life plan, or develop a new plan. She can review her contraceptive requirements and make any modifications. Once again, if a woman decides to change her method as a result of the RLP “booster”, she will be directed to contact her health care provider if it requires a prescription or procedure. If she does not have a current health care provider, the RLP intervention will direct her to a Highmark member services website from which she can find a provider practicing in her area.

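### Read literally, the denominator rule for the primary outcome keeps four periods for women who miss surveys or are lost without withdrawing consent, so those surveys count as non-use

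*Protocol*

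**What the plan says.** Section 11.3.1 builds a proportion for each woman. The numerator is "the number of time periods in which the participant's response is positive", and this is "divided by the number of time periods in which the participant is not intending pregnancy". The next sentence fixes the count: "The denominator will be four, except for those participants who withdraw consent from the study, change their minds about intending pregnancy". Pregnancy itself is the third and last exception listed. The same construction serves both binary outcomes, contraceptive use and satisfaction with the method, and the primary analysis is a binomial regression on these proportions.

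Section 11.2.1.1 defines the primary outcome as "the proportion of 6-month intervals women are reporting any contraceptive use out of the number of 6-month intervals women are not intending pregnancy". Use is asked at each assessment, and intention is also self-reported, so a missed survey supplies neither.

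Section 3.2 allows for "10% lost to follow-up per year", listed separately from women who change their minds and women who become pregnant. Section 5.2.3 describes a reminder sequence for women who have not answered. It ends with an e-mail to "alert them to the fact that the survey will be taken off line by a given date", so the protocol expects some women to miss a survey without having withdrawn.

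**The concern.** The exceptions in section 11.3.1 form a closed list of three, and silence is not on it. A woman who skips a survey, or disappears without withdrawing consent, keeps a denominator of four. A survey that was never answered cannot be positive, so it lowers her proportion exactly as a report of non-use would.

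Three things are at stake in the primary outcome. The level of use would be understated. A true effect would shrink. Any difference between arms in survey response would pass into the estimate as an apparent difference in contraceptive use. The affected group is not small by the protocol's own planning figure. Two analysts could also compute different primary outcomes, one following the definition and the other following the denominator sentence.

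**Working it through.** **1. The plan's own sample size.** Inputs from section 3.2: rates 0.25 and 0.35, two-sided level 0.025, power 90%, four time points, and three losses of 10% per year each.

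- Two-proportion formula with pooled variance: (2.241 × √(2 × 0.30 × 0.70) + 1.282 × √(0.25 × 0.75 + 0.35 × 0.65))² / 0.10² ≈ 519.01, rounded up to 520 observations per arm.
- Four periods taken as independent: 520 / 4 = 130 women.
- Losses of 30% per year over two years remove 60%: 130 / 0.40 = 325 per arm, against the stated 324.

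On this route women lost to follow-up are removed from the data along with the other two groups. They are not kept as non-users. The route is not unique: other combinations of retained periods and within-woman correlation also come near 324.

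**2. One woman under each reading.** She answers yes at 6 and 12 months and is then lost without withdrawing consent.

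| Reading | Numerator | Denominator | Score |
|---|---|---|---|
| Denominator sentence taken literally | 2 | 4 | 0.50 |
| Only periods with a reported intention | 2 | 2 | 1.00 |

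**3. Dilution.** Assume that the 10% annual loss compounds and occurs without withdrawal of consent.

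- Surveys answered, (1 − 0.10)^t at t = 0.5, 1, 1.5 and 2 years: 0.949, 0.900, 0.854, 0.810; mean 0.878.
- Recorded level when true use is 0.90 (assumed): 0.90 × 0.878 = 0.79.
- Recorded rates on the plan's inputs: 0.25 × 0.878 = 0.220 and 0.35 × 0.878 = 0.307; difference 0.088 in place of 0.10.

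**4. False difference with no true effect.** Assume use of 0.90 in both arms.

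- Equal loss: difference 0.
- Loss of 8% against 12% per year (assumed): mean completion 0.9020 and 0.8545; recorded use 0.812 and 0.769; difference 0.90 × (0.9020 − 0.8545) = 0.043.
- Periods per arm under the literal rule: only mind changes and pregnancies are removed, 20% per year over two years, so 324 × 0.60 × 4 ≈ 778.
- Standard error with independent answers: √((0.812 × 0.188 + 0.769 × 0.231) / 778) = 0.0206. With within-woman correlation 0.5, the design effect is 1 + 3 × 0.5 = 2.5 and the standard error is 0.0326.
- Rejection at two-sided 0.0167 (critical value 2.394): about 37% with independent answers and about 14% with correlation 0.5.
- Loss of 9% against 11% (assumed): difference 2.1 points, rejection about 4% to 9%.

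**The case against.** The strongest reply is that no passage says a missed survey counts as non-use. The governing definition, given in section 11.2.1.1 and again in 11.3.1, divides by periods in which the woman is not intending pregnancy. Where no survey was answered there is no recorded intention to place the period in the denominator. The sentence about four can then be read as describing when the count falls short. Its three exceptions mirror the three losses in section 3.2, with withdrawal of consent standing where that section has loss to follow-up. Section 11.3.1 also adds a shared parameter model that treats participant withdrawal as informative censoring, and further missing-data detail may sit in an SAP that is not shown.

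Much of this stands as evidence of intent. A reader might infer that the protocol adopts a policy of scoring every missed survey as non-use. The documents do not support that: it is the consequence of one sentence, other text points against it, and it does not apply to women under the three exceptions. But the sentence is explicit, and it concerns the primary outcome. The shared parameter model is a further analysis and leaves the primary proportions unchanged. The point is a stated rule that conflicts with its neighbours, which is different from missing-data detail left to an SAP.

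A reader might also infer that power falls from 90% to about 84%. That figure applies the diluted rates to about 519 periods, from which lost women have already been removed, so it counts the loss twice. With the 778 periods that the literal rule keeps, the same independence calculation gives about 95.5%. This does not make the rule harmless, because the added periods are unanswered surveys entered as zeros. It does mean that a fall below 90% is not shown.

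Finally, a reader might infer that response will differ by arm. Sessions take about 30 minutes for RLP and 45 for RLP+ (sections 7.2.1 and 7.3.1), and booster contact is described for the active arms (section 7.2.4: "the RLP group will be emailed and asked to login to the website"; section 7.3.3 is parallel). Yet reminders are described for all participants alike, and section 7.5.1 places each session after its survey, so only later surveys could be affected. Unequal loss is possible, but nothing in the protocol gives its size.

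**Conclusion.** The point holds as a defect in a stated rule. The denominator sentence omits women who miss surveys or are lost without withdrawing consent, and followed literally it scores their missed surveys as non-use. It is inconsistent with the outcome definition and, on the route that reproduces 324 per arm, with the sample size.

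If the 10% annual loss in section 3.2 is all of this kind and compounds, recorded values are 0.878 of the true ones: 0.90 becomes 0.79 and a difference of 0.10 becomes 0.088. Dilution needs no difference between arms. Bias under no effect does: it is zero with equal loss and 4.3 points with 8% against 12%, rejected in about 14% to 37% of trials instead of 1.67%. Those rates rest on assumed use of 0.90, assumed unequal loss, 778 periods per arm and within-woman correlation from 0.5 to 0. Because the rule defines the primary endpoint, it should be settled before any comparison of the arms.

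**What to change.** Replace the denominator sentence in section 11.3.1 with:

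> The denominator is the number of completed post-baseline assessments at which the participant reports not intending pregnancy and is not excluded because of pregnancy; an assessment missed for any reason, including loss to follow-up without withdrawal of consent, enters neither numerator nor denominator.

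Apply the same rule to the satisfaction proportion. The pregnancy clause must stay. Without it, a woman who is pregnant at a completed survey and reports not intending pregnancy would enter the denominator and could be counted as a non-user.

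The cost is one sentence, with no new data and no extra participants. The change also brings the analysis into line with section 11.2.1.1 and with the apparent basis of the sample size.

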### 6.2. Measures

- **Pregnancy history and pregnancy intentions and ambivalence**

We will ascertain how many times women have been pregnant in the past, as well as the outcomes of those pregnancies including number of spontaneous abortions, elective abortions, and live births. Women will be asked if they are intending future pregnancy using standard measurement, which categorizes women as intending future pregnancy, not intending future pregnancy, or ambivalent (not sure if intending future pregnancy or not). The concept of ambivalence has become increasingly important, as studies have indicated that ambivalence is associated with inconsistent contraceptive use and risk for unintended pregnancy. We hypothesize that the RLP and RLP+ interventions, which prompt women to repeatedly consider their reproductive goals, will result in decreased ambivalence. Women will also be asked how important it is to them to avoid pregnancy (very important, somewhat important, a little important, and not important) within the next year.

- **Marital and relationship history**

Relationship variables include marital/cohabiting status, relationship duration, number of sexual partners in the past 6 months, frequency of intercourse in the past 6 months ( $\geq 2x/\text{week}$ ,  $2-4x/\text{month}$ ,  $\leq 1x/\text{month}$ ), happiness with relationship, and happiness with partner's parenting (if applicable). Changes in relationship over time will be measured, as changes in partner status are expected to be key predictors of changes in pregnancy intentions and contraceptive status.

- **Sexual and contraceptive history**

Using standard measures from the NSFG, we will determine history of contraceptive methods use, as these variables have been shown to be predictors of nonadherence in previous studies.

- **Perceived control/fatalism toward contraception/preventing pregnancy**

Using a 5-point Likert scale, women will be asked if they agree/disagree with the statement, "It doesn't matter whether I use birth control or not; when it is time to get pregnant, it will happen." Our previous work has suggested that fatalism

toward contraception and preventing pregnancy may affect contraceptive adherence.

- **Health history**

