## 11.2.3. Primary Outcomes Variables (Aim 2)

### 11.2.3.1. Continuity of Contraceptive Use and Adherence

Continuity of contraceptive use describes whether women use contraception continuously, or have periods where they stop using contraception while at risk for pregnancy. Items will assess contraceptive method use throughout the preceding 6 months to determine episodes of contraceptive use, gaps in contraceptive use, and risk for pregnancy during gaps in use. Contraceptive continuation over each 6-month assessment interval will be measured using an ordinal longitudinal contraceptive use typology as described by Frost and colleagues: 1) continuous contraceptive users of one method, 2) continuous users with at least one method switch, 3) non-continuous users with gaps in use when not at risk for pregnancy, 4) non-continuous users with gaps in use when at risk for pregnancy, and 5) continuous nonusers. This typology has been shown to be associated with risk for unintended pregnancy.

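### The primary denominator is shortened for unintended pregnancies although its definition keeps them; the excluded periods are tied to non-use, and the resulting bias depends on effect scale and level of use

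*Protocol*

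**What the plan says.** All references are to the protocol; the SAP is not at hand.

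- **Outcome definition (11.2.1.1).** Each woman's result is her number of periods with any contraceptive use, "divided by the number of time periods in which the participant is not intending pregnancy". The periods end at 6, 12, 18 and 24 months. No exception for pregnancy is given here.
- **Analysis (11.3.1).** The same proportion is restated. The denominator is then said to be four except for women who withdraw consent, "change their minds about intending pregnancy during the study, or become pregnant". Intended and unintended pregnancies are not separated.
- **Sample size (3.2).** On top of 10% yearly loss to follow-up and 10% for changed intention, the plan allows "another 10% lost per year for those women who become pregnant (intentionally or unintentionally".
- **Unintended pregnancy (11.2.4.1).** A pregnancy is unintended if the woman said at the preceding interview that she did not intend pregnancy in the next year. Its incidence is an exploratory outcome, compared by arm.
- **Informative censoring (11.3.1).** A shared parameter model is planned for time to participant withdrawal. Pregnancy is not mentioned.

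**The concern.** A woman who did not intend pregnancy at one interview and conceived before the next belongs in the denominator under 11.2.1.1. Sections 11.3.1 and 3.2, read literally, take her out. The protocol does not say whether the interval in which she conceived is kept, or how it is scored.

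This matters because pregnancy follows randomisation and is linked to the outcome. Non-users conceive more often than users, so the deleted intervals contain a larger share of non-use than the retained ones. A non-user who conceives before month 6 may contribute no period to an analysis described as intention-to-treat. Neither the primary analysis, with assignment as its sole regressor, nor the withdrawal model addresses this.

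The denominator also depends on intention as reported after randomisation. Section 6.2 expects that the tools "will result in decreased ambivalence" about pregnancy, so the set of counted periods may differ between arms for that reason too.

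**Working it through.** **1. The plan's own size.** Inputs from 3.2: "972 randomized participants (324 for each of the three study groups"; "effect size of 0.10 (difference between rates of 0.25 and 0.35"; "two-sided, 0.025 significance level test (Bonferroni correction"; 90% power; four time points. The two-proportion formula gives about 520 observations per arm. 520 / 4 = 130 women. Losses of 3 × 10% × 2 years = 60% give 130 / 0.40 = 325, against the stated 324. The size therefore already treats pregnancies of both kinds as lost.

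**2. Size of the exclusion.** Per arm there are 324 × 4 = 1296 scheduled periods. Assume no return to the denominator after a pregnancy (an upper bound).

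- At 10% per year, the shares not yet pregnant at the four assessments are 0.949, 0.900, 0.854 and 0.810, sum 3.512. Lost: 324 × (4 − 3.512) ≈ 158 periods (12.2%). Pregnant before month 6: 324 × (1 − 0.949) ≈ 17 women.
- At 5.1% per year (the 51 unintended pregnancies per 1000 women cited in 11.2.4.1): about 82 periods (6.3%) and 8 women.

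The 10% includes intended pregnancies, so the second line is closer to the women for whom the rules conflict.

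**3. Effect on the comparison.** Let u be the true share using, constant within women, with yearly pregnancy risk f_u in users and f_n in non-users. With pregnant periods deleted,

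recorded use = Σ u(1−f_u)^t / Σ [u(1−f_u)^t + (1−u)(1−f_n)^t], t = 0.5, 1, 1.5, 2.

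Assumed: u = 0.80 control, 0.90 intervention; f_n = 30%, f_u = 5%, which gives 0.8 × 5% + 0.2 × 30% = 10% per year in control, as in 3.2.

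- Retention sums: users 0.975 + 0.950 + 0.926 + 0.903 = 3.753; non-users 0.837 + 0.700 + 0.586 + 0.490 = 2.612.
- Control: 0.8 × 3.753 = 3.002 use and 0.2 × 2.612 = 0.522 non-use, so 0.852.
- Intervention: 0.9 × 3.753 = 3.378 and 0.1 × 2.612 = 0.261, so 0.928.
- Difference 0.076 against a true 0.100. Odds ratio (3.378/0.261)/(3.002/0.522) = 2.25, the true value: the factor 3.753/2.612 multiplies the odds in both arms and cancels.

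The same formula with other inputs:

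| True use | f_n / f_u | Yearly pregnancy, control | Recorded use | Difference | Odds ratio (true) |
|---|---|---|---|---|---|
| 0.80 / 0.90 | 30% / 5% | 10% | 0.852 / 0.928 | 0.076 | 2.25 (2.25) |
| 0.80 / 0.90 | 15.3% / 2.55% | 5.1% | 0.826 / 0.914 | 0.088 | 2.25 (2.25) |
| 0.25 / 0.35 | 12.6% / 2.1% | 10% | 0.277 / 0.382 | 0.105 | 1.615 (1.615) |

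If the intervention also halves users' risk (5% to 2.5%, assumed), the user sum in that arm becomes 3.876. Its odds are 0.9 × 3.876 / 0.261 = 13.35 against 5.75 in control, so the odds ratio rises to 2.32, above the true 2.25.

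**4. What keeping the conception interval does.** The exponents become 0, 0.5, 1 and 1.5. The sums are 3.851 (users) and 3.122 (non-users). Recorded use is 0.831 and 0.917, difference 0.086. For precision, count each woman's four periods as one observation because use is constant. The standard error of the log odds ratio is √Σ(1/count), with counts 324 × share / 4.

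- Deletion: 243.2, 42.3, 273.6, 21.2, giving 0.280.
- Conception interval kept: 249.5, 50.6, 280.7, 25.3, giving 0.259.

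**The case against.** **Scale.** The link for the binomial regression is not named, and the longitudinal analyses are logistic. On the logit scale nothing is biased if risk depends only on use. This stands, but precision is still lost, and 3.2 states its target as a difference.

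**Level of use.** The protocol's only rates are 0.25 and 0.35, where the difference does not shrink. That also stands. Against it, the outcome counts any method, including withdrawal, and Table 2 gives 85% first-year pregnancy without a method. At 25% use, non-users alone would then give 0.75 × 85% ≈ 64% per year, far from the planned 10%. Not all enrolled women are continuously at risk, so this is rough, but it suggests higher use.

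**The text can be read benignly.** Section 11.3.1 does not say which periods go. Keeping the conception interval and dropping later pregnant ones is compatible with it, and leaving out periods when a woman is pregnant is reasonable for this outcome. Scoring detail may sit in the SAP. This limits the point to a conflict to be resolved, but the conflict is in the protocol's own definition of its primary outcome.

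**Stronger readings a reader might infer.**

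- That contraceptive failures are deleted. The outcome is use, not pregnancy: conception during use is a yes, so deleting that interval removes a success. The pregnancies themselves remain in the exploratory outcome.
- That affected women vanish. Those who conceive after month 6 keep their earlier periods.
- That Table 2 rates can be put in directly. With 85% and 9%, the formula gives a difference of only 2.3 points. But this implies 0.8 × 9% + 0.2 × 85% = 24% yearly pregnancy in control, against the plan's 10%.

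**Conclusion.** The denominator rules conflict for unintended pregnancies. Under the literal reading of 11.3.1 and 3.2, intervals tied to non-use are excluded after randomisation, and no planned analysis covers this. The exclusion is at most about 6% to 12% of scheduled periods per arm, at 5.1% to 10% yearly pregnancy.

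The documents do not support a general statement that the intervention effect shrinks:

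- If pregnancy risk depends only on use, the odds ratio is unchanged and precision falls.
- The risk difference shrinks when use is common: 10 points become about 7.6 at 10% yearly pregnancy, or 8.8 at 5.1%, for assumed use of 0.80 against 0.90.
- At 0.25 against 0.35 the difference is slightly larger (0.105).
- If a tool also lowers users' pregnancy risk, the odds ratio is biased upwards.

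These figures rest on assumed use levels, a 6:1 risk ratio, use that is constant within women, and no return after pregnancy. An unknown direction is itself a reason to fix the rule before the data are seen.

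**What to change.** In 11.2.1.1 and 11.3.1, state that the interval in which a pregnancy not intended at the preceding interview begins stays in the denominator. Score it by use or non-use at conception, and drop only later pregnant intervals. The data are already planned: for Aim 2, "Items will assess contraceptive method use throughout the preceding 6 months" (11.2.3.1). In the illustration, the recorded difference moves from 0.076 to 0.086 against a true 0.10, and the standard error falls from 0.280 to 0.259.

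Add a sensitivity analysis in all randomised women with the outcome *not using while not intending pregnancy* (yes/no) at each assessment. Women who intend pregnancy count as no, so the denominator no longer depends on intention reported after randomisation.

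The cost is analysis wording and no new data collection. The drawback is that use at conception is recalled over up to six months.
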